Use of Electroconvulsive Therapy to Treat Self-Injurious Behavior in Adults with Autism Spectrum Disorders

I. Overview:

Self-injurious behavior (SIB) is one of the strongest predictors of psychiatric hospitalization among children with Autism Spectrum Disorder (ASD) aged 5 to 21 years. While self-injury in some patients is operant-based, involuntary self-injury can be a presentation of catatonia. When psychopharmacologic interventions fail, electroconvulsive therapy (ECT) is a safe and highly effective alternative to treating catatonia and major depression. Given that catatonia may present as SIB, especially in patients with ASD, several case studies have used ECT to minimize the self-injury in treatment-resistant patients. This study will use formal measures, including the Aberrant Behavior Checklist (ABC), Repetitive Behavior Scale (RBS), and the Self-Injury Trauma (SIT) Scale to monitor the outcome of using ECT to treat SIB in patients with ASD, for whom psychotropic medication has not worked. This study will be fundamentally different from the previously published literature on the subject in that this will be a prospective study which will aim to recruit multiple participants in an open label study.

II. Specific Aims and Hypotheses:

SIB in ASD is both physically and emotionally damaging to patients. Many patients with SIB who have ASD are treatment resistant in regard to psychopharmacologic treatment. ECT has been reported as an effective treatment for SIB in ASD but only through case reports. The major aim of this research study is to provide prospective research data of the efficacy of ECT in this population.

Specific Aim 1: Clarification, verification, and characterization of the presence of SIB in ASD subjects prior to ECT, through the use of the Self Injury Trauma Scale and daily caregiver assessments of self-injurious behavior.

Specific Aim 2: To measure the efficacy of ECT on SIB by comparing clinical, physical, and psychological signs and symptoms pre and post ECT using the Self-injury Trauma Scale, Repetitive Behavior Scale-Revised, Aberrant Behavior Checklist, ASD Diagnostic Checklist, and the caregiver's daily diary card.

Hypothesis 2: ECT will be an effective treatment for SIB as measured by improvements in the Self-injury Trauma Scale, Repetitive Behavior Scale-Revised, Aberrant Behavior Checklist, and the daily diary card, kept by the caregiver. ECT will not lead to significant changes in the ASD Diagnostic Checklist.

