For this study, all adult individuals presenting to EVMS Psychiatry and Behavioral Sciences will be considered for this clinical treatment study if they have a documented ASD diagnosis by a psychiatrist or psychologist. Participants (N=20) must be over the age of 18, and must have an LAR who can consent to medical treatment and attend all appointments with the participant. Only the participant's LAR may consent to treatment (no participants in this study will be permitted to self-consent). Those individuals considered wards of the state will be considered for the study as long as they meet all inclusion/exclusion criteria and are able to follow through with all steps of the protocol (e.g., guardianship, consent, transportation, etc.). Additionally, the participant must have a present history of self-injurious behavior (SIB) that significantly impacts their quality of life, for which they have tried and failed at least four other treatment methods in the past. SIB is any behavior "which produces injury to the individual's own body." (Tate and Baroff, 1966). All subjects must be medically cleared per the clinical ECT protocol already in place, which includes obtaining an EKG, Chest X-Ray (CXR), Complete Metabolic Panel (CMP), and Complete Blood Count (CBC). Subjects must also obtain a head CT scan. All studies must be less than 6 months old. Additionally, subjects must receive a full clinical psychiatric evaluation with the principal investigators: [name], MD to evaluate for appropriateness for and response to ECT and [name], MD to evaluate for ASD symptoms in subjects prior to, during, and at follow-up.

Study Design

This study design is single subject design over multiple participants. Any patient who is enrolled for ECT with a diagnosis of ASD and SIB that meets inclusion and exclusion criteria will be entered into the study if their guardian/subject provides consent/assent. All ECT procedures will be performed at the SNGH outpatient surgical suite.

Procedure

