After the individual has been screened and is determined to meet the inclusion and exclusion criteria they will be scheduled for two pre-treatment appointments and sent a consent form to review ahead of time. As part of the inclusion and exclusion criteria, the participant must have an appointment with their primary care provider or a hospital internist to complete a physical exam and required tests (EKG, CXR, CMP, CBC, and head CT scan). At the first pre-treatment appointment (Visit 1), the participant and their legal guardian will go over the consent form with the investigator. In addition to the consent form, to be signed by the legal guardian, the

participant will receive an assent of the cognitively impaired. After giving consent, the legal guardian will be given a Sentara release of medical information form so that investigators will have access to the ECT-performing physician's medical notes. The guardian or other caregiver will then fill out the ASD Diagnostic Checklist, Repetitive Behavior Scale- Revised, and the Aberrant Behavior Checklist. The physician will complete the Self-Injury Trauma Scale, which documents the number, type, and severity of unhealed self-injury traumas. At the end of the Visit 1, the guardian/ caregiver will receive a Subject Diary Card to record the number of self-injury episodes per day, the number of aggressive episodes per day, and the perceived severity of episodes that day. The Diary Card also has space to record the medication taken by the participant every day.

The second pre-treatment appointment (Visit 2) will consist of a complete psychiatric evaluation with review of all medical evaluations. The subject must receive medical clearance as defined by Sentara Norfolk General Hospital to undergo ECT treatment. The first Diary Card will be collected at this time, and a second Diary Card will be given.

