After receiving medical clearance, or "low risk" to undergo ECT, participants (accompanied by their guardians/ caregiver) will begin to receive ECT treatments. They will receive ECT 3 times a week for 4 weeks, for a total of 12 treatments (Visits 3- 14). All ECT treatments will take place in the Outpatient Surgery and Diagnostic Unit of Sentara Norfolk General, and will be performed by [name] or [name]. All subjects will receive bilateral "brief" ECT, based on the potential risk that self-injurious behavior holds. Participants will be placed under general anesthesia (Etomidate) and after it is determined that the anesthesia is in effect they will be given a primary muscle relaxant (Succinylcholine). Patients will receive one bag of IV NS fluids. An anesthesiologist or nurse anesthetist will hyperventilate the patient to lower their seizure threshold. Two electrodes will be placed bi-temporally. An electric current will pass through the electrodes to the brain through a process of conduction. During initial treatment (Visit 3), the total amount of energy will be titrated until a short seizure is produced, which is called seizure threshold. During subsequent visits (Visits 4-14), the settings will be adjusted to a total energy of 2.5 x seizure threshold, as determined by the ECT provider. Electrical activity in the brain, including seizure quality, duration, and post-ictal suppression of seizure, will be determined by electroencephalogram (EEG). Throughout the procedure, the provider will be monitoring blood pressure, heart rate, and oxygen saturation. While asleep, the participant will be given oxygen through an oxygen mask and a bite block will be placed to protect the teeth and tongue during stimulation. Following the procedure, the patient will recover in the Post Anesthesia Care Unit.

Throughout the course of the treatment, guardians/ caregiver will continue filling out the Diary Card. Once treatment begins, guardians/ caregiver will be asked to also include any side effects of the treatment noted by themselves or the participant. Guardians/ caregiver will turn in and receive new Diary Cards at Visit 3, Visit 6, Visit 9, and Visit 12. After Visit 14, patients will begin to receive maintenance ECT as prescribed by the ECT physician.

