After acute ECT treatment is complete, patients and their guardians/ caregiver will return to EVMS Department of Psychiatry and Behavioral Sciences for post-treatment appointments (Visits 15-18). At these post-treatment appointment guardians/ caregiver will complete the ASD

Diagnostic Checklist, Repetitive Behavior Scale- Revised, and the Aberrant Behavior Checklist. The physician will complete a second Self-Injury Trauma Scale. At this time the Diary Card will be collected and subjects will receive Diary Cards for 1 month. Visits 15-18 will occur at 1 month, 2 months, 6 months, and 12 months post – acute ECT treatment. See the next page for a timeline summary of visits.

		Appointment Type	To-Do	Diary Card
Week 1	Visit 1	Pre- ECT Appointment	Consent and Assent forms, Release of Medical Information, ADC, RBS-R, ABC, Self-Injury Trauma Scale	Receive Diary Card 1
Week 2	Visit 2	Pre- ECT Appointment	Psychiatric Evaluation, Medical Clearance	Return DC 1, Receive DC 2
Week 3	Visit 3	ECT	Determine Seizure Threshold	Return DC 2; Receive DC 3
	Visit 4	ECT	Treatment	
	Visit 5	ECT	Treatment	
Week 4	Visit 6	ECT	Treatment	Return DC 3; Receive DC 4
	Visit 7	ECT	Treatment	
	Visit 8	ECT	Treatment	
Week 5	Visit 9	ECT	Treatment	Return DC 4; Receive DC 5
	Visit 10	ECT	Treatment	
	Visit 11	ECT	Treatment	
Week 6	Visit 12	ECT	Treatment	Return DC 5; Receive DC 6
	Visit 13	ECT	Treatment	
	Visit 14	ECT	Treatment	
Week 7	Visit 15	Post- ECT visit	ADC, RBS-R, ABC, Self-Injury Trauma Scale	Return DC 6; Receive DC 7, 8, 9, 10
Week 11	Visit 16	Post- ECT visit	ADC, RBS-R, ABC, Self-Injury Trauma Scale	Return DC 7, 8, 9, 10
6 Months	Visit 17	Follow-up visit	ADC, RBS-R, ABC, Self-Injury Trauma Scale	
12 Months	Visit 18	Follow-up visit	ADC, RBS-R, ABC, Self-Injury Trauma Scale	

Measures

Self-Injury Trauma Scale (SIT) allows differentiation and quantification of self-injury. In conjunction with a complete medical assessment, the physician records location of injury, type of injury, number of injuries, and an estimate of severity. Given these findings a Number Index, Severity Index, and Estimate of Current Risk can be calculated. The scale has been shown to have high interrater reliability.⁴

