Information concerning the potential side effects of ECT will be discussed with the subject/legal guardian/ caregiver so that the subject has sufficient understanding. All subjects and guardians/ caregiver will be given information on how to contact the co-investigators should they have any questions or problems concerning ECT side effects. All interviews and questionnaires have been widely and safely used with diverse populations. All questionnaires and written research materials will be kept in a locked file room. All information will be identified only with numerical codes (rather than identifying information such as a name). To protect against risks, all subjects must be medically cleared per the clinical ECT protocol already in place, which includes obtaining an EKG, Chest X-Ray (CXR), Complete Metabolic Panel (CMP), and Complete Blood Count (CBC). Subjects must also obtain a head CT scan. These tests will help determine if a subject is at an increased risk for an adverse effect. Patients with preexisting cardiac illness, compromised pulmonary status, a history of brain insult or medical complications after earlier courses of anesthesia are likely to be at an increased risk, but will not be excluded from the study as none of these complications are absolute contraindications. The treatment team will be capable of managing the major classes of cardiovascular complications, including cardiac arrest, arrhythmias, ischemia, hypertension, and hypotension. To protect against prolonged seizures, the first treatment will determine the seizure threshold of the patient and following treatments the patient will receive the lowest affective dose. The team will be capable of dealing with instances of prolonged apnea, prolonged or tardive seizures, and status epilepticus. Participants will be monitored on an electroencephalogram (EEG) during the procedure. Vital signs will be continually monitored before, during and after each ECT procedure, and patients will only leave the recovery area once the vital signs are stable. Muscle relaxants are administered to protect the subject from fractures or dislocations. A mouth guard will be placed in the participant's mouth prior to induction of the seizure to protect against oral/dental trauma. At every treatment patients and their caregivers will be questioned by the psychiatrist to determine that ECT treatment is not exacerbating any psychological symptoms, such as mania. Given the nature of the risks, all

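### The protocol does not say whether or when the outcome scales and the open diary card are collected from participants who stop ECT before session 12

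*Protocol*

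**What the plan says.** Specific Aim 2 (protocol, section II) measures efficacy by "comparing clinical, physical, and psychological signs and symptoms pre and post ECT". Hypothesis 2 expects improvement on four measures: the Self-Injury Trauma Scale (SIT), the Repetitive Behavior Scale-Revised (RBS-R), the Aberrant Behavior Checklist (ABC) "and the daily diary card, kept by the caregiver". The ASD Diagnostic Checklist (ADC) is expected not to change significantly. The study is open label, without a control group, and has 20 participants (section IV, Inclusion and exclusion criteria: "Participants (N=20) must be over the age of 18").

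The Procedure text and the visit table in section IV set the data collection:

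- **Baseline scales.** At Visit 1: "The guardian or other caregiver will then fill out the ASD Diagnostic Checklist, Repetitive Behavior Scale- Revised, and the Aberrant Behavior Checklist". The physician completes the SIT at the same visit.
- **Acute course.** "They will receive ECT 3 times a week for 4 weeks, for a total of 12 treatments", which are Visits 3-14. None of the four scales is scheduled at Visits 2-14.
- **Post-treatment scales.** "After acute ECT treatment is complete, patients and their guardians/ caregiver will return to EVMS" for Visits 15-18, where all four scales are repeated.
- **Diary cards.** "Guardians/ caregiver will turn in and receive new Diary Cards at Visit 3, Visit 6, Visit 9, and Visit 12". The table adds Visit 15 for the sixth card, and Visit 16 for the four cards handed out at Visit 15.

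There is no early-termination visit, and no statement on whether assessment continues or ends for a participant who does not reach session 12.

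**The concern.** Each step assumes that session 12 is reached. Post-baseline scales depend on completing the acute course, and diary exchange depends on attending particular ECT sessions. A participant who leaves the course early can therefore fall out of both streams without anyone departing from the protocol.

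Early stopping is foreseeable from the document. At every treatment, patients and caregivers are "questioned by the psychiatrist to determine that ECT treatment is not exacerbating any psychological symptoms, such as mania" (Protection against Risks). The same section keeps people at raised cardiac, pulmonary or neurological risk eligible. Attendance also depends on a legally authorized representative coming to every appointment.

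People who stop for worsening, intolerance or lack of benefit would probably show less improvement than those who finish. With no control group, nothing else in the trial would reveal that selection. Caregiver-recorded side effects after stopping, which bear on Specific Aim 3, could also be lost. This is a matter of data collection: an analysis plan can choose a population or a missing-data method, but it cannot supply scales that were never completed.

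**Working it through.** The protocol states no power calculation, dropout rate or effect size, so there is no figure to reproduce. The check is a trace of the schedule, followed by an illustration under stated assumptions.

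**Step 1. What an early stopper has, by last session.** Session k takes place at Visit k + 2. Card DC3 is issued at Visit 3 and due at Visit 6. DC4 is issued at Visit 6 and due at Visit 9, DC5 at Visit 9 and due at Visit 12, and DC6 at Visit 12 and due at Visit 15.

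| Last session (visit) | Treatment-period cards returned on schedule | Card still open | Its return visit | Scales after Visit 1 |
|---|---|---|---|---|
| 1-3 (Visits 3-5) | none | DC3 | 6, not reached | none assured |
| 4-6 (Visits 6-8) | DC3 | DC4 | 9, not reached | none assured |
| 7-9 (Visits 9-11) | DC3, DC4 | DC5 | 12, not reached | none assured |
| 10-11 (Visits 12-13) | DC3, DC4, DC5 | DC6 | 15, not assured | none assured |
| 12 (Visit 14) | DC3, DC4, DC5 | DC6 | 15 | Visits 15-18 |

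For example, if the last ECT is at Visit 7 (session 5), DC3 came back at Visit 6. DC4, which covers the days around stopping, is due at Visit 9. All of SIT, RBS-R and ABC, three of the four measures expected to improve, depend on whether Visits 15-18 are held.

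**Step 2. Whether the calendar settles it.** The text places Visits 15 and 16 at 1 and 2 months after acute ECT. The table places them in Weeks 7 and 11. The last ECT week is Week 6, so the table gives 7 - 6 = 1 week and 11 - 6 = 5 weeks after acute ECT. The two disagree even for a completer, so neither can serve as an unambiguous rule for a stopper.

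**Step 3. Possible size.** Let p be the fraction who stop early without a post-baseline scale, M the completers' mean change, and rM the stoppers' mean change. Then

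all-treated mean = (1 - p)M + p·rM = M[1 - p(1 - r)],

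and completer mean / all-treated mean = 1/[1 - p(1 - r)]. With r = 0 this is 1/(1 - p).

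All values of p and r below are assumptions:

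| p (of 20) | r = 0 (no change) | r = 0.5 | r = 1 | r = 1.5 |
|---|---|---|---|---|
| 10% (2) | 1/0.90 = 1.11 | 1/0.95 = 1.05 | 1.00 | 1/1.05 = 0.95 |
| 20% (4) | 1/0.80 = 1.25 | 1/0.90 = 1.11 | 1.00 | 1/1.10 = 0.91 |
| 30% (6) | 1/0.70 = 1.43 | 1/0.85 = 1.18 | 1.00 | 1/1.15 = 0.87 |

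If stoppers got worse (r below 0), the ratio exceeds the r = 0 column. Each participant lost is 1/20 = 5% of the sample.

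**The case against.** The strongest reply is that the protocol excludes nobody. *Complete* can mean ended, and the trigger sentence does not itself mention 12 treatments. The table gives Visits 15-18 calendar labels, so a site could hold them for someone who stopped. **This stands in part.** It shows silence rather than exclusion. It does not remove the gap, because the only acute course described is the 12-session one and the calendar labels conflict with the text.

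A reader might infer that the efficacy result will cover completers only. The document does not support that. It states no analysis population, a choice that belongs to the statistical analysis plan, which is not shown. The diary is a named efficacy measure and gives on-treatment data on schedule for anyone who reaches session 4.

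A reader might also infer that stoppers leave the safety record. That is not supported either. Investigators obtain access to the ECT physician's notes through the release form (Procedure). Families are told how to contact the co-investigators about side effects (Protection against Risks). Reporting of serious adverse events does not depend on finishing the course. What may be lost is mainly non-serious effects that the caregiver would have recorded after stopping.

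Finally, the protocol calls the serious complications rare or infrequent and never says that they end a course, so no rate of early stopping can be read from it.

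**Conclusion.** The point holds as a gap in planned data collection. For a participant who stops ECT after any of sessions 1-11, no post-baseline SIT, RBS-R, ABC or ADC is assured and the open diary card has no assured return. After a stop within sessions 1-3, no treatment-period card has come back on schedule. The uncontrolled pre/post comparison therefore risks being limited to completers.

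The direction and size of any bias cannot be established from the document. The factors of 1.11 to 1.43 rest on two assumptions: that 10-30% stop early, and that they show no change. Partial improvement brings the factor towards 1, and stopping because of early benefit could take it below 1. The figures illustrate why the gap is worth closing. They are not an estimate for this trial.

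**What to change.** 1. In the Procedure text on post-treatment appointments, state that Visits 15-18 and their scales apply to everyone who received at least one ECT, whether or not all 12 treatments were given.
2. First reconcile the text (1 and 2 months after acute ECT) with the table (Weeks 7 and 11). Then express the chosen timing on one calendar counted from Visit 3, with stated offsets for all four visits, so that it applies equally to stoppers and completers. Counted from Visit 3 in Week 3, the table's labels are 7 - 3 = 4 and 11 - 3 = 8 weeks; the text implies later dates. Which timing is intended is for the sponsor to settle.
3. In the Procedure text and the table, issue and collect diary cards by study week instead of ECT visit number, so that they continue after ECT stops.
4. Record the number of ECT sessions received, the date of the last one and the reason for stopping.

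The analysis population can be left to the statistical analysis plan. When ECT should stop is a clinical matter not addressed here.

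The cost is protocol wording and a few extra visits using existing forms and staff. Some who stop will decline to return, so the gap may narrow without closing, and the reported effect may be less favourable.

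### Diary Cards 1-6 are handed in about weekly but Cards 7-10 in one batch about four weeks after issue, so the pre- versus post-ECT diary comparison is made under different collection conditions

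*Protocol*

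**What the plan says.** Section II, Hypothesis 2, lists the outcomes expected to improve. The list ends "Aberrant Behavior Checklist, and the daily diary card, kept by the caregiver", so the diary is an efficacy measure, though one of several and not named as primary. Section IV, Procedure, says that the caregiver uses the card to "record the number of self-injury episodes per day, the number of aggressive episodes per day, and the perceived severity of episodes that day". It is the only day-by-day count of self-injury in the protocol.

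Hand-in before and during ECT is frequent. At Visit 2, "The first Diary Card will be collected at this time, and a second Diary Card will be given". During the acute course, "Guardians/ caregiver will turn in and receive new Diary Cards at Visit 3, Visit 6, Visit 9, and Visit 12". In the visit table these exchanges fall in Weeks 2 to 6.

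After the acute course the arrangement changes. The text says "At this time the Diary Card will be collected and subjects will receive Diary Cards for 1 month". The table entry for Visit 15 (Week 7) reads "Return DC 6; Receive DC 7, 8, 9, 10" and that for Visit 16 (Week 11) reads "Return DC 7, 8, 9, 10". No diary is issued after that.

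The text and table disagree on when Visit 15 takes place. The table puts it in Week 7, the week after the last acute treatment. The text says "Visits 15-18 will occur at 1 month, 2 months, 6 months, and 12 months post – acute ECT treatment".

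**The concern.** A pre/post comparison of a caregiver-kept count is sound only if the count is taken in the same way on both sides. Here the hand-in interval lengthens from about one week to about four, and it does so at the boundary between acute treatment and follow-up. With weekly hand-in, staff can see a blank or implausible day while the caregiver may still remember it. With a four-week batch they cannot, and a card filled in from memory shortly before Visit 16 looks the same as one kept daily.

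The study is open label and has no concurrent control, so no comparison group shows the effect of the change in collection alone. Episodes left off the later cards but not the earlier ones would lower the post-ECT count, which is the direction Hypothesis 2 predicts. At stake is how far a fall on DC 7-10 can be credited to treatment.

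**Working it through.** **1. Hand-in interval, from the visit table (return week minus issue week).**

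| Card | Phase | Issued | Returned | Interval |
|---|---|---|---|---|
| DC 1 | pre-ECT | Week 1 | Week 2 | 1 week |
| DC 2 | pre-ECT | Week 2 | Week 3 | 1 week |
| DC 3 | acute ECT | Week 3 | Week 4 | 1 week |
| DC 4 | acute ECT | Week 4 | Week 5 | 1 week |
| DC 5 | acute ECT | Week 5 | Week 6 | 1 week |
| DC 6 | acute ECT | Week 6 | Week 7 | 1 week |
| DC 7-10 | post-acute | Week 7 | Week 11 | 4 weeks |

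The batch return of DC 7-10 does not depend on which timing of Visit 15 is meant. Visits 15 and 16 are about a month apart in the table (Weeks 7 and 11) and in the text (1 and 2 months). The weekly return of DC 6 does depend on it. Under the text, DC 6 is issued at Visit 12 and not collected until about a month after Visit 14, so it too is returned late.

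**2. Effect of a change in recording.** The protocol gives no recording rates, so the fractions below are assumptions. Let r_pre and r_post be the fractions of true episodes written down. With no true change:

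apparent reduction = 1 − r_post / r_pre

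- 95% to 85%: 1 − 0.85/0.95 = 10.5%
- 95% to 75%: 1 − 0.75/0.95 = 21.1%
- 90% to 60%: 1 − 0.60/0.90 = 33.3%
- no change in recording: 0%

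The result depends only on the ratio of the two fractions, not on N or the episode rate.

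**3. Does the handling of blank days matter?** This was checked by simulation with no true effect. Assumptions: N=20; 14 pre-ECT days, fully recorded; 28 post-ECT days; mean 5 or 10 episodes a day; overdispersed counts; days blank at random; paired t-test at two-sided 0.05; 2,000 runs per setting. The last two columns give the chance of a significant fall.

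| Post-ECT days blank | Apparent reduction, blank = 0 | Chance, blank = 0 | Chance, blank = missing |
|---|---|---|---|
| 0% | about 0% | 0.02-0.03 | 0.02-0.03 |
| 10% | 9-10% | 0.15-0.17 | about 0.02 |
| 20% | about 20% | 0.54-0.56 | about 0.02 |
| 30% | about 30% | 0.87-0.90 | 0.02-0.03 |
| 40% | about 40% | 0.99 | 0.02-0.03 |

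With blanks treated as missing, the apparent reduction is about 0% in every row. Wholly blank days therefore do harm only if they are read as zero, or if they are not missing at random. Step 2 still applies to episodes left off a day that was filled in, which no rule for blank days can restore.

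**The case against.** The strongest reply is that the schedule is uneven but harm is not shown. Most of that stands.

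- **Recording may not worsen.** A reader might infer that monthly return will degrade the diary. Nothing in the protocol shows this, and the fractions above are illustrations.
- **Direction.** A reader might infer that back-filling always favours ECT. Recalled counts can be too high or too low. Only omission has a definite direction. Weekly hand-in also permits some back-filling, so the contrast is one of degree.
- **Blank days.** The card asks for a daily number, so a blank is not a zero, and the protocol nowhere says it should be counted as one. The rule may be in a SAP that was not available, and its absence from the protocol is not criticised here.
- **Other evidence.** A reader might infer that nothing in the data could separate an artefact from benefit. That goes too far. By the table, DC 1-2 and DC 3-6 share weekly hand-in, so a fall already present on DC 3-6 cannot come from the later change. The SIT scale is completed by the physician, and the RBS-R and ABC at visits, so diary collection does not affect them. These checks are partial: a further fall starting at DC 7 coincides both with the change in collection and with the move to maintenance ECT, and the visit-based scales are not daily counts.
- **Contact.** A reader might infer that families are out of contact between Visits 15 and 16. Maintenance ECT begins after Visit 14, and the section on protection against risks has the psychiatrist question patients and caregivers at every treatment. The frequency is left to the ECT physician, however, and no diary hand-in or check is attached to it.

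**Conclusion.** The point holds as a difference in measurement conditions. By the table, the hand-in interval is one week for DC 1-6 and four weeks for DC 7-10, and the change falls on the pre/post diary contrast. The protocol describes nothing that offsets it.

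The consequence is conditional. If recording falls after ECT, the apparent reduction equals the proportional loss in recording: 10.5% to 21.1% for a fall from 95% to 85% or 75%, and zero if recording holds. The protocol does not say which applies. It does not support the conclusion that the diary result will be biased, or that the efficacy assessment as a whole fails. Only the comparison of pre-ECT cards with DC 7-10 is affected on the table's timing, with DC 6 added on the text's timing.

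This is a worthwhile low-cost improvement. It belongs in the protocol because the collection schedule is fixed there, and analysis cannot identify late-filled days or recover omitted episodes afterwards.

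**What to change.** 1. Have each of DC 7, 8, 9 and 10 returned at the end of its own week, by prepaid envelope or by hand if the participant is on site. The hand-in interval is then one week in every phase.
2. Make one brief reminder contact in each of those weeks.
3. Add a tick box to all cards, including DC 1-6, for any day filled in later than the next day. Late entries can then be counted in each phase and set aside in a sensitivity analysis.
4. Reconcile the timing of Visit 15 between table (Week 7) and text (1 month after acute ECT), and state the period DC 6 covers and when it is returned.

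Cost: 4 cards × 20 participants = 80 mailings at most, a few minutes of coordinator time per week, and a small revision to the card and procedures. No extra visit is needed. Cards list daily medication, so posted cards should carry only the study number, in line with the protocol's confidentiality provisions. Caregivers also note side effects on the card once treatment begins, so weekly return would bring in that information for Aim 3 sooner.
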